4. STUDY POPULATION

4.1 Population

We plan to randomize 316 patients. All adult patients admitted to the hospital with cellulitis (see definition in appendix I) will be eligible for inclusion. The cohort comprises 316 subjects to be recruited by the Departments of Infectious Disease and Dermatology at the Academic Medical Center, the VU Medical Center and the University Medical Center Utrecht in collaboration with 8 affiliated teaching hospitals as mentioned above. These hospitals provide secondary and tertiary care to a large heavily populated urban region of the Netherlands. Participating hospitals have declared that they expect to admit at least 20 suitable cellulitis patients yearly. Assuming that 75% of patients will partake in this study, this brings the estimated recruiting period to approximately 3.5 years (396 patients / (8 centers * 15 patients yearly) = 3.3 years → this number has been adjusted to 316 as of July 2015, which puts the estimated deadline at April 2017). A dedicated research nurse will help with patient enrolment.

If during the enrolment process it is expected that the recruiting period will last longer than 3.5 years, additional hospitals will be approached to participate in the study. The number of inclusions will be evaluated on at least a yearly basis.

As control group for the microbiota analysis from the skin swabs (see 7.3.6), we will include 20 healthy volunteers who are age- and gender-matched to the population of whom the skin swabs are analysed. Eligible volunteers are aged 18 or older, and should not have had cellulitis, abscesses, dermatitis, or psoriasis in their leg in the past 3 months. The rest of the protocol is not applicable to these volunteers, except when specifically mentioned. These patients will have completed their participation in this study, as soon as the skin swab has been taken.

4.2 Inclusion criteria

In order to be eligible to participate in this study, a subject must meet all of the following criteria. Subjects must be:

- Admitted to the hospital to receive intravenous antibiotics for cellulitis/erysipelas. Cellulitis is the general descriptive term suggesting infection and indicating the warmth, erythema and induration of skin and/or subcutaneous tissue, with or without pain (this also includes erysipelas, see appendix I).
- 18 years of age or older
- Capable of giving written informed consent and able to comply with the requirements and restrictions listed in the informed consent form

4.3 Exclusion criteria

As this study focuses on the treatment of cellulitis requiring hospitalization without additional complicating factors, a potential subject who meets any of the following criteria will be excluded from participation:

- Allergy for flucloxacillin, other beta-lactam antibiotics or one of the additives, or flucloxacillin induced hepatitis or liver enzyme disorders.
- Concurrent use of antibiotics for other indications
- Alternative diagnosis accounting for the clinical presentation.
- All cases involving any of the following complicating factors:
 - o Use of antibiotics with Gram-positive activity for more than 4 days in the past 7 days
 - o Intensive care unit admission during the last 7 days
 - o Risk factors associated with Gram-negative pathogens as a causative agent¹⁹:
 - o Chronic or macerated infra-malleolar ulcers, or infra-malleolar ulcers with previous antibiotic treatment, in patients with diabetes mellitus²⁰
 - o Neutropenia
 - o Cirrhosis (Child-Pugh class B or C)
 - o Intravenous drug use
 - o Human or animal bite
 - o Skin laceration acquired in fresh or salt open water
 - o Fish fin or bone injuries
 - o Severe peripheral arterial disease (Fontaine IV)
 - o Severe cellulitis necessitating surgical debridement or fascial biopsy
 - o Necrotizing fasciitis
 - o Periorbital or perirectal involvement
 - o Surgery
 - o Life expectancy less than one month

4.4 Sample size calculation

The sample size calculation of is based on three large randomised clinical trials which were published in high impact journals in 2014. From the DISCOVER, ESTABLISH and SOLO trials, information was gathered on cellulitis clinical cure rates as assessed by investigators after therapy:

DISCOVER²¹ (dalbavancin vs vancomycin-linezolid): (information from supplementary data)

- Clinical status evaluation at the end of therapy (day 14) of cellulitis patients:
 - o Cured: 297/324 and 276/301

ESTABLISH²⁷ (tedizolid vs linezolid): (information received from authors via e-mail)

- Investigator assessed response at post-therapy evaluation (7-14 days after end of therapy) of cellulitis patients:
 - o Cured: 265/301 and 263/307

SOLO²⁸ (oritavancin vs vancomycin): (information received from authors via e-mail)

- Investigator assessed clinical cure rates at the post-therapy evaluation (7-10 days after end of therapy) of cellulitis patients:
 - o Cured: 294/387 and 315/400

Total cure rates:

- $$(297+276+265+263+294+315) / (324+301+301+307+387+400) = 1710 / 2020 = 84,65\% \text{ cure rate}$$

A two-group large-sample normal approximation test of proportions with a one-sided 0.050 significance level will have 80% power to reject the null-hypothesis, assuming a success rate

of 85% and considering a difference of 10% between the two groups as equivalence limit, if the sample size of each group is 158. This gives a total sample size of 316 patients.

5. TREATMENT OF SUBJECTS

5.1 Investigational product/treatment

After 5-6 days of treatment, patients who respond to therapy – defined as absence of fever (defined as temp $> 38.0^{\circ}\text{C}$) and clinical improvement since admission (either self-reported or investigator-assessed using the cellulitis severity score) – will be randomized in a blinded fashion with a 1:1 allocation ratio to receive 6 more days of (A) oral flucloxacillin or (B) oral placebo (both starting after day 6):

- (A) Regular treatment group: after the initial 6 days of flucloxacillin, another 6 days of oral flucloxacillin.
- (B) Intervention group: after the initial 6 days of flucloxacillin, 6 days of oral placebo.

Flucloxacillin treatment is administered as currently advised by the SWAB⁹: flucloxacillin intravenously 1000mg 4dd or orally 500mg 4dd, as a minimum. Some physicians will decide to dose differently, such as intravenously 1000mg 6dd, or orally 1000mg 4-6dd. This is allowed, but will be documented and can be taken into account during the analyses. No added benefit is to be expected from higher or more frequent dosing. Empirical treatment on admission can differ from flucloxacillin, provided it contains a beta-lactam antibiotic with anti-staphylococcal activity. Switch from intravenous medication to the oral route can be initiated before the 6th day of treatment at the discretion of the attending physician, but only if the patient has no fever (temp $> 38.0^{\circ}\text{C}$) and when the physician is convinced the cellulitis is improving. Patients who do not respond to treatment or whose blood cultures became positive (excluding contamination related positive blood cultures) will not be randomized and will be treated at the discretion of the attending physician. Their definitive diagnosis upon discharge, definitive antibiotic treatment and discharge date will be recorded.

5.2 Use of co-intervention

Other treatment will not be different from daily practice (e.g. diet, contraception, other therapies). Compression therapy should be encouraged, but is not obligatory, and is at the discretion of the attending physician.

5.3 Escape medication

Not applicable.

5.4 Adherence to investigational treatment

As there are only 6 days of trial medication use, we don't expect there to be issues with adherence. Nevertheless, patients will be thoroughly informed about the necessity of adherence to trial medication. To register the rate of adherence, patients will be asked how many capsules of the trial medication they have left at day 14-15. Reasons for non-adherence will be recorded.

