6.5 Description and justification of route of administration and dosage

1. See SPC of flucloxacillin, paragraph 4.2. The 500 mg capsules will be administered orally four times/day, as the SWAB guidelines dictate⁹. Some physicians might alter dosing within a certain range as per the "Farmacotherapeutisch Kompas", this will be documented but allowed, although a minimum of 4dd 1000mg i.v. and 4dd 500mg p.o. are maintained.
2. These capsules should likewise be administered orally four times/day.

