6.6 Dosages, dosage modifications and method of administration

1. With diminished kidney function (creatinine clearance <10 ml/min or hemodialysis): 500 mg orally every 8 hours.
2. Identical dosage modifications for placebo: one capsule every 8 hours.

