9. STATISTICAL ANALYSIS

9.1 General considerations

For the modified intention to treat analysis, all randomized patients who received at least one dose of study medication will be included. Missing data will be handled with multiple imputation, due to its nature of giving standard errors and P values that incorporate missing-data uncertainty²².

For the per protocol analyses, only randomized patients whose compliance was clear, and who received at least four days of trial medication (in clinical successes), or one day of trial medication (in clinical failures) will be included.

For the per protocol analysis of our primary outcome, patients are considered clinically cured if there is resolution of cellulitis at 14 days defined as disappearance of warmth and tenderness at the site of infection, with substantial improvement in erythema and edema, and without recurrence by day 28, defined as the need of additional antibiotic therapy for cellulitis. Clinical failure is defined as the persistence or progression of signs and symptoms of the acute process after randomization, or the inability to complete the study owing to adverse events. The response is deemed indeterminate when the patient (i) received less than 80% of the study drug for reasons other than clinical failure, (ii) acquired a concomitant infection outside of the skin requiring antibiotic treatment, (iii) was lost to follow-up, or (iv) died unrelated to the primary diagnosis.

For the per protocol analysis of our first secondary outcome (paragraph 7.1.2), patients are considered clinically cured if there is resolution of cellulitis at 14 days, defined as the absence of fever and an improvement of the combined symptom score of warmth, tenderness, erythema and edema by 2 or more points since patient inclusion (or it has reached 0), and without recurrence by day 28, defined as a stable or further improved combined symptom score, absence of fever and no need of additional antibiotic therapy for cellulitis. The response is deemed indeterminate when the patient (i) received less than 80% of the study drug for reasons other than unblinding / requiring new antibiotics for cellulitis / being unable to continue due to adverse effects, (ii) acquired a concomitant infection outside of the skin requiring antibiotic treatment, (iii) was lost to follow-up, or (iv) died unrelated to the primary diagnosis. Those whose outcomes are not cured or indeterminate are considered clinical failures.

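### Per-protocol adherence rests on an unverified patient report of capsules left; a staff count at the existing day 14-15 visit would be cheap and less open to bias

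*Combined protocol and SAP*

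**What the plan says.** Protocol 5.4 starts from the view that "As there are only 6 days of trial medication use, we don't expect there to be issues with adherence". The measure itself is that "patients will be asked how many capsules of the trial medication they have left at day 14-15", and "Reasons for non-adherence will be recorded". It describes no count by staff, no return of capsules and no date of last dose. Section 6.8 adds one general commitment to drug accountability under GMP guidelines, without linking it to any analysis variable.

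Section 9.1 uses adherence in two ways:

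- Entry to the per-protocol set: "only randomized patients whose compliance was clear, and who received at least four days of trial medication (in clinical successes"; for clinical failures, one day is enough. What makes compliance clear is not defined.
- Response classification: for the primary outcome, a response is indeterminate if the patient "received less than 80% of the study drug for reasons other than clinical failure". The first secondary outcome has a similar 80% rule with a different list of exceptions.

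The daily number of capsules is not the same for everyone. Section 6.5 says "The 500 mg capsules will be administered orally four times/day" but also "Some physicians might alter dosing within a certain range". Section 6.6 has, for reduced kidney function, "Identical dosage modifications for placebo: one capsule every 8 hours".

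Table 3 in 9.4 lists the per-protocol analysis among the sensitivity analyses, under a non-inferiority hypothesis, with a chi-squared test and a relative risk.

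**The concern.** In a non-inferiority trial the per-protocol set is a check against dilution: if control patients do not take the control treatment, the arms become alike and non-inferiority is easier to show. Here the control treatment is the second six days of flucloxacillin. A 12-day patient who stops early, but reports few or no capsules left, has had something close to the short course and is still analysed as adherent. Participants are randomised because they have already improved, so early stopping is plausible, although the documents give no rate for it.

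The check is therefore only as good as an unverified answer given once, after the course has ended. The plan also does not say how that answer becomes a number of days or a percentage, and the same leftover number means different things on different schedules.

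**Working it through.** **1. The plan's own figures.** Section 4.4 assumes 85% success, a 10-point margin, one-sided 0.05 and 80% power. The unpooled normal approximation gives n = 2 × 0.85 × 0.15 × (1.645 + 0.842)² / 0.10² = 157.7, so 158 per group and 316 in total, as stated. Nothing below changes this.

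**2. Do capsules left convert to the two rules?** Yes, once the number supplied and the daily number are known. Over six days:

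- Four a day: 6 × 4 = 24 scheduled. Four days = 16 taken, so at most 8 left. 80% of 24 = 19.2, so 20 taken and at most 4 left.
- One every 8 hours: 6 × 3 = 18 scheduled. Four days = 12 taken, so at most 6 left. 80% of 18 = 14.4, so 15 taken and at most 3 left.

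The schedule matters. If supply equals schedule (an assumption), 4 capsules left is 20/24 = 83.3% on the first schedule and passes 80%; it is 14/18 = 77.8% on the second and fails.

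**3. Do the two rules agree?** No. Four of six days is 4/6 = 66.7%. A success with 16 to 19 of 24 capsules taken satisfies the four-day rule but, unless an exception applies, is indeterminate under the 80% rule.

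**4. How much misreporting moves one patient?** Someone on four a day who stops after three days has 12 left. Reporting 8 passes the four-day rule; reporting 4 passes both.

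**5. Effect on the comparison (illustration).** Assumptions:

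- With full adherence, cure is 85% (12-day, from 4.4) and 75% (6-day, i.e. a true difference at the 10-point margin).
- A fraction q of each arm stops before four days but after at least one. The values of q are assumed.
- Early stoppers cure at 75% in either arm, so the extra days they took bring no benefit.

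If all of them are reported as adherent, cure is 0.85 − 0.10q against 0.75, and the difference is 0.10(1 − q).

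If they are counted accurately under the four-day/one-day inclusion rule, early-stopping successes leave and early-stopping failures stay. Cure is then 0.85(1 − q)/(1 − 0.75q) against 0.75(1 − q)/(1 − 0.75q).

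| q | Misreported: 12-day, 6-day, difference | Counted: 12-day, 6-day, difference | Change in difference (points) |
|---|---|---|---|
| 5% | 84.5%, 75.0%, 9.5 | 83.9%, 74.0%, 9.9 | 0.4 |
| 10% | 84.0%, 75.0%, 9.0 | 82.7%, 73.0%, 9.7 | 0.7 |
| 15% | 83.5%, 75.0%, 8.5 | 81.4%, 71.8%, 9.6 | 1.1 |

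For q = 10% the counted figures are 0.765/0.925 and 0.675/0.925. If instead the 80% rule removed every early stopper, the counted difference would be 10.0 and the change 0.5, 1.0 and 1.5 points.

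On the relative-risk scale of Table 3 (6-day over 12-day), the counted value is 0.75/0.85 = 0.882 throughout. Misreported it is 0.75/0.845 = 0.888, 0.75/0.840 = 0.893 and 0.75/0.835 = 0.898. The shift is small and always towards 1.

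The 6-day arm also moves, from 75.0% to 73.0% at q = 10%, because the inclusion rule depends on outcome. The last column therefore reflects the count and the rule together, not dilution alone.

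**The case against.** The strongest case on the other side has four parts.

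- **The report can be converted.** Capsules left, supply and schedule do give percent and equivalent days. The plan documents altered dosing (5.1, 6.5), and 7.2 refers to accountability list entries, so supply is likely on record. This stands: a reader might infer that the measure cannot establish the thresholds at all, and step 2 shows that it can. What remains is accuracy and an unwritten formula.
- **There are safeguards.** Entry requires clear compliance, reasons for non-adherence are recorded, 11.1 draws medication data from hospital records and questionnaires, and 6.8 promises accountability. Nothing forbids looking at the capsules at the visit. These are partial: clear compliance has no criterion, and no count is tied to 9.1.
- **No error rate follows.** A reader might put the diluted difference through the 4.4 test, with 158 per arm and a 10-point margin, and quote an inflated type I error. The documents do not support that. Table 3 assigns this set a chi-squared test and a relative risk with no margin, 158 is the full randomised arm, and the misreporting rate would be invented.
- **The effect is not confined to one arm.** A reader might infer that misreports under placebo change nothing. Under the four-day/one-day rule they do change the placebo cure rate, as step 5 shows. The net direction in that illustration is still towards non-inferiority.

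It is also fair to say that a count does not detect discarded capsules.

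**Conclusion.** The point holds as a cheap improvement to measurement. The only adherence measure described is an unverified report, it decides who meets two rules in 9.1, and over-reporting would pull the per-protocol comparison modestly towards non-inferiority. In the illustration the difference changes by about 0.4 to 1.1 points for 5% to 15% early stoppers, or 0.5 to 1.5 points if the 80% rule governs. Those sizes rest on assumed stopping rates, on every early stopper being reported as adherent, on a true difference at the margin, and on no benefit from the extra days taken. If early stoppers in the 12-day arm lost nothing by stopping, misreporting would leave the difference at 10.0.

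The consequence is limited to the per-protocol sensitivity analyses. The modified intention-to-treat result and the sample size are unaffected. The mismatch between four days (66.7%) and 80% needs no assumption; it is in the text of 9.1.

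**What to change.** - In 5.4, have the investigator count the remaining capsules at the day 14-15 visit and record the date of the last capsule. Under 3.3 that visit is already face to face, and under 5.5 it is primarily at home.
- Derive adherence as supplied minus counted. Divide by that patient's own scheduled total for percent, and by the scheduled daily number for days. Use this one variable for both rules in 9.1.
- Where the capsules are not available to count, use the patient's report and flag it.
- In 9.1, state what makes compliance clear, and reconcile the four-day rule with the 80% rule so that a success with 16 to 19 of 24 capsules taken has one defined status.

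Cost: one count at a visit already made and two eCRF fields, with no change to treatment, visits or sample size. Some containers will be missing, and discarded capsules will still be read as taken.

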5.5 Retention of participants

Once enrolled, every reasonable effort to follow the participant until the end of study will be made by the investigators. To diminish possible loss to follow-up due to travelling, we primarily visit patients at home for follow-up assessments, but also extend the offer to visit our outpatient clinic.

6. INVESTIGATIONAL PRODUCT

6.1 Name and description of investigational products

1. Flucloxacillin tablet 500 mg capsule, ATC code J01CF05
2. Placebo capsule, currently being procured by dr. [name], hospital pharmacist and trial medication specialist

6.2 Summary of findings from non-clinical studies

1. See Summary of Product Characteristics (SPC) of flucloxacillin, paragraph 5.3.
2. Once finished, this will be available in the placebo's IMPD.

6.3 Summary of findings from clinical studies

1. See SPC of flucloxacillin, paragraph 5.1.
2. Not applicable.

6.4 Summary of known and potential risks and benefits

1. See SPC of flucloxacillin, paragraph 4.4 through 4.9. The most frequently seen side effects are gastro-intestinal upset or skin rash, occurring in 0,1-1% of the patients.
2. Not applicable.

6.5 Description and justification of route of administration and dosage

1. See SPC of flucloxacillin, paragraph 4.2. The 500 mg capsules will be administered orally four times/day, as the SWAB guidelines dictate⁹. Some physicians might alter dosing within a certain range as per the "Farmacotherapeutisch Kompas", this will be documented but allowed, although a minimum of 4dd 1000mg i.v. and 4dd 500mg p.o. are maintained.
2. These capsules should likewise be administered orally four times/day.

6.6 Dosages, dosage modifications and method of administration

1. With diminished kidney function (creatinine clearance <10 ml/min or hemodialysis): 500 mg orally every 8 hours.
2. Identical dosage modifications for placebo: one capsule every 8 hours.

6.7 Preparation and labelling of Investigational Medicinal Product

Preparation and labelling of study drugs will be done according to the relevant GMP guidelines by the AMC trial pharmacy.

6.8 Drug accountability

Drug accountability will be done according to the relevant GMP guidelines.

7. METHODS

7.1 Study endpoints

7.1.1 Main study endpoint

The primary endpoint is resolution of cellulitis at 14-15 days, defined as disappearance of warmth and tenderness at the site of infection, with substantial improvement in erythema and edema, and without recurrence by day 28-29, defined as the need of additional antibiotic therapy for cellulitis.

This endpoint is in accordance with the study by Hepburn et al¹², and assumes that erythema and edema take longer to resolve than warmth and tenderness as seen in clinical practice.

7.1.2 Secondary study endpoints

- Resolution of cellulitis at 14-15 days, defined as the absence of fever and an improvement of the combined symptom score of warmth, tenderness, erythema and edema by 2 or more points since patient inclusion (or it has reached 0), and without recurrence by day 28-29, defined as a stable or further improved combined symptom score, absence of fever and no need of additional antibiotic therapy for cellulitis.
 - A per protocol analysis of this endpoint (see paragraph 9.1).
 - Sensitivity analyses with two modifications to the day 28 criteria:
 - Resolution of cellulitis at 14 days, defined as the absence of fever and an improvement of the combined symptom score of warmth, tenderness, erythema and edema by 2 or more points since patient inclusion (or it has reached 0), and with further improvement of the combined symptom score of 1 or more point(s) (or it has reached 0), absence of fever, and no need of additional antibiotic therapy for cellulitis by day 28
 - Resolution of cellulitis at 14 days, defined as the absence of fever and an improvement of the combined symptom score of warmth, tenderness, erythema and edema by 2 or more points since patient inclusion (or it has reached 0), and with further improvement of the combined symptom score of 2 or more point(s) (or it has reached 0), absence of fever, and no need of additional antibiotic therapy for cellulitis by day 28
- Recurrence of cellulitis by day 90 after inclusion, defined as the need of additional antibiotic therapy for cellulitis
- Speed of recovery, as determined by improvement in cellulitis severity score, and self assessment of subjective pain and swelling on Visual Analog Scales scales (0-10), assessed at baseline (day 0), days 2-3, 5-6, 14-15, 28-29 and 90 (day 90 self-assessment only)¹²
- Mean health-related Quality of Life (using the Dutch SF-36 questionnaire and the EQ-5D) at day 0, 28-29 and 90.

- Health care resource utilisation, as determined by total antibiotic use and effect on direct and indirect health-care associated costs

